### **5.5 Concomitant Medications**

WHO Drug Dictionary Version 2018:03 will be used to classify concomitant medications by therapeutic class. A concomitant medication is defined as any medication with the start date prior to the date of the first dose of investigational product and continuing after the first dose of investigational product or with a start date between the dates of the first and last doses of investigational product, inclusive. Medications started before study dosing, but continuing after are considered as both prior and concomitant medications.

All concomitant medications will be listed for the Safety Set.

## 5.6 Exposure to Investigational Product

All exposure data will be listed for the Safety Set. In addition, for each subject the following data will be listed:

- Days of dosing in Part 1
- Days of dosing in Part 2A
- Days of dosing in Part 2B
- Last study day of dosing

If subjects have their dose escalated to 360 mg/day separate information will be supplied for each dose. This will also be done if subjects change their dose for any other reason, with rows of the listing being in chronological order.

## 5.7 Measurements of Treatment Compliance

Compliance for Part 1, 2A, 2B and overall, based on the percentage of days they took study medication prior to discontinuation/completion will be listed for the Safety Set. Compliance is calculated as the number of days the subject took the investigational product divided by the duration the subject was in the study. If the investigator instructed the subject to stop taking the investigation product for a period of time e.g. due to an adverse event, then this period will not be included in the denominator for the compliance calculation.

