9. STUDY PROCEDURES

Please see the Study Flow Chart in [Section 2](#) for a summary of the schedule of study participation and procedures. The schedule of visit dates should be established, either, prior to, or at the time of screening allowing subjects an opportunity to assess whether there are likely to be significant conflicts with other activities or planned absences. To the extent possible, subjects will be expected to adhere to the visit schedule and any re-scheduling of visits must be agreed, in advance, with the investigator and sponsor to ensure that the dosing of study medication can continue daily as required.

If a subject's dose is increased beyond 270 mg/day in Part 2B additional site visits will be scheduled for the first 6 weeks of dose increase, alternating with the monthly visits in the protocol.

i.e. subjects will return to the clinical site every two weeks for 6 weeks. These will be scheduled by the investigator and the same procedures as the monthly visits will be performed. These visits will be recorded as unscheduled visits.

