9.5.1 Exit Visit (Day 414, or Day 134, or Day 78)

All subjects will be asked to return to the clinical facility for the Exit Visit 7 weeks after the final dose of APL-2.

Study participation for each subject will be concluded following completion of the Exit Visit.

Subjects that complete Part 2B and Part 3 of the study will attend an Exit Visit on Day 414.

Subjects that are not eligible to enter Part 2B but complete Part 2A of the study will attend an Exit Visit on Day 134. Subjects that are not eligible to enter Part 2A but complete Part 3 of the study will attend an Exit Visit on Day 78. If a subject withdraws from the study prior to the scheduled Exit Visit, all Exit Visit evaluations should be performed at the subject's final visit to the clinic, including the collection of blood samples for PK and/or PD assessments, as well as a post-dose antigenicity sample if not yet collected.

The Exit Visit procedures are listed in the Study Flow Chart in [Section 2](#).

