considers that the subject is both capable and confident to conduct self-administration. The subject will continue to self-administer infusions at the clinic on those days when a clinic visit occurs (Day 8, 15 and 22) and at an off-site location convenient to the subject on all other days up to Day 28 in Part 1. Following review of available safety, PK and PD data by the investigator and sponsor subjects demonstrating clinical benefit from the treatment may progress to Part 2A of the study and continue to receive daily doses of APL-2 until Day 84, and then may progress to Part 2B of the study and continue to receive daily doses of APL-2 until Day 364. Doses will be self-administered throughout this period at an off-site location convenient to the subject with the exception of Days 29, 36, 43, 57, 71, 85, 113, 141, 169, 197, 225, 253, 281, 309, and 337 where dosing is performed by the subject at the clinical site. If a subject has a sub-optimal clinical response during daily dosing with 270 mg APL-2, the dose may be increased up to 360 mg/day during part 2A, and doses will be administered at the clinical site every 2 weeks for the first 6 weeks after commencing the higher dose. After the conclusion of the treatment period (Day 364), subjects will enter Part 3 of the study and return to the clinical site for follow-up study procedures on Day 365, 379, and 393 and final study procedures at an Exit Visit on Day 414. If a benefit is observed an extension study will be considered and will be submitted as a further protocol amendment or as a follow-up study

The planned length of participation in the study for each subject is approximately 444 days (from Day -30 through completion of the Day 414 Exit visit procedures). Interim PK and PD analyses may be performed to reconsider the sampling time points as the study progresses.

An independent Safety Monitoring Committee (SMC) will assess the progress and cumulative safety/tolerability data of the study on a regular basis.

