## **5. STUDY SUBJECTS**

### **5.1 Disposition of Subjects**

A listing of all Screen Failures (i.e., subjects who were screened but not dosed) will be presented along with reasons for screen fail.

Disposition data, including whether the subject entered Parts 1, 2A, 2B and 3 with the corresponding start dates (and study day) will be listed. If a subject withdrew during the study then the reason for withdrawal will also be listed.

A listing of the analysis sets the subjects are included in will be presented.

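### SAP 5.7 is internally inconsistent: the lead-in describes compliance over the dosing parts, but the formula divides by time in the study, which includes 50 planned off-drug days

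*SAP*

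**What the plan says.** SAP 5.7 first describes what will be listed for the Safety Set: "Compliance for Part 1, 2A, 2B and overall, based on the percentage of days they took study medication prior to discontinuation/completion". The next sentence gives the only formula: "Compliance is calculated as the number of days the subject took the investigational product divided by the duration the subject was in the study". One kind of time is then removed from the denominator, namely periods when the investigator told the subject to stop taking the product. Screening and follow-up are not mentioned.

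Other sections fix how long a subject is in the study:

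- Protocol 9.5.1: "Study participation for each subject will be concluded following completion of the Exit Visit". For subjects who complete Part 2B that visit is on Day 414.
- SAP 3.1: "After the conclusion of the treatment period (Day 364), subjects will enter Part 3 of the study". Follow-up is therefore off drug but still part of the study.
- SAP 3.1: "The planned length of participation in the study for each subject is approximately 444 days", counted from Day -30 to the Day 414 visit.
- Flow chart footnote M (Protocol 2 and SAP 17.1): a subject who stops dosing early moves into Part 3, so stopping the drug does not end time in the study.

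**The concern.** The lead-in and the formula in SAP 5.7 do not describe the same quantity. The lead-in names only the three dosing parts and their overall value. The formula's denominator, taken at its word, also covers the follow-up in Part 3, when no dose is planned. The SAP has a more suitable term available: SAP 13.5.2 speaks of treatment duration, tied to the last date on which the product was taken. SAP 5.7 does not use it.

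What is at stake is how a listed figure is read. With 4 subjects reported individually, each compliance percentage will be taken as a fact about that subject. A denominator that includes planned off-drug time makes full adherence look like missed doses, and nothing in the value shows which of the two it is.

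**Working it through.** **Inputs**

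- Dosing days for a completer, from the part boundaries in SAP 3.1 (Days 28, 84, 364): 28 + (84 - 28) + (364 - 84) = 28 + 56 + 280 = 364.
- Exit Visit for a completer: Day 414 (Protocol 9.5.1, SAP 3.1).
- Screening: up to 30 days before Day 1 (SAP 3.1).
- Study day 1 is the first dosing day (SAP 13.1), so Day 1 to Day 414 is 414 days.

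**The plan's own figure.** Participation from Day -30 to Day 414, with no Day 0, is 30 + 414 = 444 days. This matches the stated length of about 444 days. The documents state no compliance percentage to reproduce.

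**Off-drug days in the literal denominator.** 414 - 364 = 50.

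**Overall compliance, completer, no missed dose**

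| Denominator | Calculation | Result |
|---|---|---|
| Treatment period (lead-in) | 364/364 | 100% |
| Day 1 to Exit Visit (formula read literally) | 364/414 | 87.9% |

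**What 87.9% looks like.** On a treatment-period denominator, 87.9% corresponds to 364 × (1 - 364/414) = 364 × 50/414 = 44.0 missed doses out of 364.

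**With some missed doses.** Assume 20 missed doses, for illustration. The treatment-period value is 344/364 = 94.5% and the literal value is 344/414 = 83.1%. The understatement remains.

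**Extreme case.** If a full 30-day screening period were also counted as time in the study, the first example becomes 364/444 = 82.0%.

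**The case against.** The strongest reply is that the paragraph answers the point itself. The section is about treatment compliance. Its first sentence limits the measure to days before discontinuation or completion and names only dosing parts. Part 3 is absent, whereas SAP 5.1 names it when it is meant: "whether the subject entered Parts 1, 2A, 2B and 3 with the corresponding start dates (and study day) will be listed". Overall, placed after Parts 1, 2A and 2B, reads naturally as their total.

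The literal reading also fails when applied consistently. For a fully dosed completer it gives 28/414 = 6.8% for Part 1, 56/414 = 13.5% for Part 2A and 280/414 = 67.6% for Part 2B. No programmer would accept those values, and one who uses each part's own duration may well carry that through to the overall value and arrive at 100%. Finally, SAP 1 places the listing specifications in a separate document, which may define the denominator.

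Most of this stands as evidence of intent, and it limits how far the point can be taken. A reader might infer that a fully adherent completer will be listed at 87.9%, or even at 82.0%. The documents do not support that. The 87.9% holds only if the formula is followed to the letter for the overall value. The 82.0% needs a full 30-day screening period in the denominator as well, and nothing in SAP 5.7 points to screening days.

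The reply does not remove the inconsistency. Completion in the lead-in is not defined, and Protocol 9.7 equates study completion with the Exit Visit. The formula is the only operational rule in the section, and it names time in the study. The exclusion of investigator-instructed stops shows that the authors meant to remove time when dosing was not expected, yet nothing removes Part 3.

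**Conclusion.** The point holds as an inconsistency within SAP 5.7: the formula conflicts with its own lead-in. If it is applied literally to the overall value, a completer with no missed dose is listed at 87.9% instead of 100%. The probable intent is a treatment-period denominator, and what will actually be listed cannot be known from these documents.

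The figure rests on nominal visit days and on a subject who completes all parts. SAP 1 says that the 4 enrolled subjects were allowed to complete the study, not that all of them did.

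The severity is minor. Compliance is a by-subject listing in an abbreviated report on 4 subjects. SAP 5.6 lists the dosing days in each part and the item "Last study day of dosing", so a reader can recompute the value. No analysis set is defined by compliance, and no efficacy, safety, PK or PD result changes.

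**What to change.** Replace the denominator in SAP 5.7 with wording such as: *the number of days in the treatment period of that part (for overall, the sum over those of Parts 1, 2A and 2B that the subject entered), based on actual dates, up to completion or discontinuation of treatment, minus investigator-instructed interruptions; screening and Part 3 are excluded.*

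Actual dates are preferable to nominal day ranges because visits can move: Protocol 9 says that "any re-scheduling of visits must be agreed, in advance, with the investigator and sponsor". The sentence should also say which recorded date marks completion of treatment in the last part entered. Using the last dosing day alone would hide doses missed at the very end.

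The cost is a sentence or two and no new data. Part start dates are already listed under SAP 5.1, and dosing days with the last dosing day under SAP 5.6. SAP 1 allows amendments before database lock. After lock, the denominator actually used can be stated in the clinical study report. The listing specifications should be checked against the revised sentence.

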## 5.8 Protocol Deviations

Protocol deviations will be recorded by the site separately from the clinical database. The CRO/Apellis will classify major and minor protocol deviations per the agreed protocol deviation management plan. The Apellis study team will review the protocol deviations and their classification throughout the study and before database lock.

Confirmed major and minor protocol deviations will be documented in the Protocol Deviation tracker for the study. Major/minor protocol deviations will be listed for the Safety Set.

## 6. EFFICACY ANALYSES

All efficacy analyses will be based on the ITT Set. For each efficacy variable, the last value collected before the first dose of investigational product will be used as baseline for all analyses of that efficacy variable.

## 6.1 Analyses of Primary Efficacy Endpoints

Individual LDH, haptoglobin and hemoglobin will be listed together with changes from baseline and percentage changes from baseline by study part and study visit. For LDH the value relative to the upper limit of normal (ULN) (i.e. value/ULN) will also be presented and for haptoglobin and hemoglobin values relative to the lower limit of normal (LLN) (i.e. value/LLN) will also be presented.

Absolute values, changes from baseline and percentage changes from baseline will be summarized, using descriptive statistics, by part of the study and study visit. The number and percentage of subjects  $\leq 1X$  ULN and  $\leq 1.5X$  ULN for LDH will also be summarized by part of the study and study visit. The number and percentage of subjects  $\geq 1X$  LLN for haptoglobin and hemoglobin will also be summarized by part of the study and study visit.

Absolute values, changes from baseline and percentage changes from baseline will be plotted by study day with each subject being identifiable. A dotted line will be used to identify follow-up (Part 3). The actual sampling day will be used on the x-axis. The changes and percentage changes from baseline plots will include a reference line for 0 on the y-axis.

Values of LDH, reticulocytes and total bilirubin related to their ULN (i.e. value/ULN) throughout the study will be plotted against time for each subject individually (i.e. one plot per subject). Hemoglobin and haptoglobin values will also be included but related to their LLN (i.e. value/LLN). Each parameter will have a different symbol and a legend will identify the parameters included. A reference line of 1 on the y-axis will be included. On study transfusions (Packed Red Blood Cells [PRBC] only) will be identified on the plot as a vertical line at the relevant study day. Above the profile plot a separate plot will be displayed which shows the APL-2 dose by study day. The study day on both plots will be aligned.

## 6.2 Analyses of Secondary Efficacy Endpoints

### 6.2.1 FACIT Fatigue Scale

Absolute FACIT fatigue scores will be listed together with changes from baseline by study part and study visit.

Absolute values and changes from baseline will be summarized, using descriptive statistics, by part of the study and study visit.

Absolute values and changes from baseline will be plotted by study day with each subject being identifiable. A dotted line will be used to identify follow-up (Part 3). The actual sampling day will be used on the x-axis. The change from baseline plots will include a reference line for 0 on the y-axis.

Values of FACIT fatigue scores throughout the study will be plotted against time for each subject individually (i.e. one plot per subject). On study transfusions (PRBC only) will be identified on the plot as a vertical line at the relevant study day. Above the profile plot a separate plot will be displayed which shows the APL-2 dose by study day. The study day on both plots will be aligned.

### **6.2.2 Reticulocytes and Total Bilirubin**

Each parameter will be listed together with changes from baseline and percentage changes from baseline by study part and study visit. The value relative to the ULN (i.e. value/ULN) will also be presented.

Absolute values, changes from baseline and percentage changes from baseline will be summarized, using descriptive statistics, by part of the study and study visit. The number and percentage of subjects  $\leq 1X$  ULN and  $\leq 1.5X$  ULN will also be summarized by study visit.

Absolute values, changes from baseline and percentage changes from baseline will be plotted by study day with each subject being identifiable. A dotted line will be used to identify follow-up (Part 3). The actual sampling day will be used on the x-axis. The changes and percentage changes from baseline plots will include a reference line for 0 on the y-axis.

### **6.2.3 RBC Transfusions**

All transfusion data will be listed by study part and study visit.

### **6.2.4 Linear Analog Scale Assessment (LASA) for Quality of Life**

Absolute values for the 3 LASA questions and the combined score (sum of the 3 individual LASA questions) will be listed together with change from baseline by study part and study visit.

Absolute values and changes from baseline will be plotted by study day with each subject being identifiable. A dotted line will be used to identify follow-up (Part 3). The actual

sampling day will be used on the x-axis. The change from baseline plots will include a reference line for 0 on the y-axis.

Values of LASA combined scores throughout the study will be plotted against time for each subject individually (i.e. one plot per subject). On study transfusions (PRBC only) will be identified on the plot as a vertical line at the relevant study day. Above the profile plot a separate plot will be displayed which shows the APL-2 dose by study day. The study day on both plots will be aligned.

## 7. SAFETY ANALYSIS

The safety analysis will be performed using the Safety Set. Safety variables include AEs, clinical laboratory variables, vital signs, and ECG variables. For each safety variable, the last value collected before the first dose of investigational product will be used as baseline for all analyses of that safety variable.

All safety analyses will be conducted according to the treatment the subject actually received.

### 7.1 Adverse Events

AEs will be coded using MedDRA Version 21.0.

An AE (classified by preferred term) that occurs during the treatment phase will be considered a treatment-emergent AE (TEAE) if it has a start date on or after the first dose of investigational product or if it has a start date before the date of the first dose of investigational product, but increases in severity on or after the date of the first dose of investigational product. If more than one AE with the same preferred term is reported before the date of the first dose of investigational product, then the AE with the greatest severity will be used as the benchmark for comparison to the AEs occurring during the treatment phase under the preferred term. An AE that occurs more than 30 days after the date of the last dose of investigational product will not be counted as a TEAE.

An overall summary of the number of subjects with TEAEs will be presented, including the number and percentage of subjects with any TEAEs, serious TEAEs, TEAEs related to investigational product and TEAEs leading to discontinuation of investigational product.

The number and percentage of subjects reporting TEAEs will be tabulated by system organ class (SOC) and preferred term. TEAEs considered related to investigational product will also be summarized by SOC and preferred term. If more than one AE occurs with the same

preferred term for the same subject, then the subject will be counted only once for that preferred term using the most related occurrence for the summarization by relationship to investigational product.

Summary tables will be presented over the whole study and by study part. AEs will be categorized by the Part in which the AE started i.e. an AE which began during Part 1 will be categorized under Part 1 even if it continues into Part 2A (unless it increases in severity during Part 2A, when it will be counted in both Parts 1 and 2A). Summaries will be ordered by descending order of total events.

All TEAEs will be listed by subject and start date. Separate listings of serious TEAEs and TEAEs leading to discontinuation of study drug will also be generated. The listing will also include duration of AE, the part of the study the AE started and the part of the study the AE stopped.

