11. ADVERSE EVENTS

11.1 Definitions

An adverse event (AE) is any untoward medical occurrence associated with the use of a drug in humans, whether or not considered drug related. An AE can therefore be any unfavorable and unintended sign, including a clinically significant abnormal laboratory finding, symptom, or disease temporally associated with the use of a study drug, whether or not considered related to the study drug.

Adverse events include the onset of new illness and the exacerbation of pre-existing conditions. Any medical condition that is present at the time that the subject is screened should be recorded on the medical history eCRF and not reported as an AE. However, if that condition deteriorates or severity changes at any time during the study, it should be recorded as an AE.

Any AEs that occur prior to dosing on Day 1 will be categorized as pre-treatment events. Treatment-emergent adverse events (TEAEs) will be defined as those AEs that occur after dosing on Day 1 and up to 30 days after the last dose of study medication.

A suspected adverse reaction means any AE for which there is a reasonable possibility that the drug caused the AE. Reasonable possibility means there is evidence to suggest a causal relationship between the drug and the AE.

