11.3.1 Intensity

The PI will determine the severity of each AE. AEs will be graded according to the Common Terminology Criteria for Adverse Events (CTCAE) version 4.03. The following definitions for rating severity will be used:

Grade 1	Mild; asymptomatic or mild symptoms; clinical or diagnostic observations only; intervention not indicated.
Grade 2	Moderate; minimal, local or noninvasive intervention indicated; limiting age-appropriate instrumental Activities of Daily Living (ADL)*.
Grade 3	Severe or medically significant but not immediately life-threatening; hospitalization or prolongation of hospitalization indicated; disabling; limiting self-care ADL**. Note: An experience may be severe but may not be serious, e.g., severe headache).
Grade 4	Life-threatening consequences; urgent intervention indicated.
Grade 5	Death related to AE

- A semi-colon indicates ‘or’ within the description of the grade.
- *Instrumental ADL refer to preparing meals, shopping for groceries or clothes, using the telephone, managing money, etc.
- **Self-care ADL refer to bathing, dressing and undressing, feeding self, using the toilet, taking medications, and not bedridden.

When changes in intensity of an AE occur more frequently than once a day, the maximum intensity for the event should be noted for that day. Any change in severity of signs and/or symptoms over a number of days will be captured and recorded as a new AE, with the amended severity grade, and the date and time (if known) of the change.

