12.2.3.1 Adverse Events

Treatment emergent adverse events (TEAE) are defined as those AEs that develop or worsen after the first dose of study medication and up to 30 days beyond the last dose of study medication. The current version of Medical Dictionary for Regulatory Activities (MedDRA) will be used to classify all AEs.

TEAE will be summarized by system organ class and preferred term. Tabulations will be produced for all TEAEs, for those considered potentially treatment related (causality to study drug is reported as possibly or probably, or where causality is not reported) and for TEAE of special interest. Number of subjects reporting SAEs will also be tabulated.

A by-subject TEAE data listing, including verbatim term, preferred term, treatment, severity, and investigator judgment of relationship to treatment, will be provided.

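### SAP 7.1 departs from the protocol's TEAE definition in two narrow, undeclared ways: a date-only rule on the dosing day, and a worst-same-term benchmark for worsening

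*SAP*

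**What the plan says.** Protocol 12.2.3.1 defines TEAEs as "those AEs that develop or worsen after the first dose of study medication and up to 30 days beyond the last dose". It has no comparison with other events of the same preferred term. Protocol 11.1 adds: "Any AEs that occur prior to dosing on Day 1 will be categorized as pre-treatment events". Protocol 11.2 collects the onset time of each adverse event when it is known.

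SAP 7.1 gives two routes to TEAE status, joined by *or*. The onset route takes an event "if it has a start date on or after the first dose of investigational product". The worsening route takes an event that starts before the date of the first dose "but increases in severity on or after the date of the first dose of investigational product". A further sentence applies once two or more events of one preferred term were reported before the first-dose date: "then the AE with the greatest severity will be used as the benchmark for comparison to the AEs occurring during the treatment phase". The comparison is made within that preferred term. Both documents end the TEAE window 30 days after the last dose.

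Protocol 11.3.1 also matters here. For a severity change across several days, the rule is that it "will be captured and recorded as a new AE, with the amended severity grade, and the date and time (if known) of the change".

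SAP section 15 explains its changes from the protocol only by the reduced set of analyses after enrollment closed at 4 subjects. It mentions neither the Day 1 rule nor the benchmark.

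**The concern.** The number and severity of TEAEs are the protocol's primary safety endpoint (Protocol 5.2), so the rule that decides what is a TEAE should be the protocol's rule, or the departure should be declared.

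Two features of SAP 7.1 work in opposite directions. The date-only rule can bring in an event that began before any drug was given. Blood samples are drawn before dosing on Day 1, so such an event is possible. The benchmark can remove an event that did worsen on drug. It compares the event with the most severe earlier event of the same term, even if that earlier event was a separate episode that had resolved, rather than with the event's own severity at first dose.

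The second direction is the less comfortable one for a safety table, because it under-counts.

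**Working it through.** The plan states no figure on this point, so there is none to reproduce. The check sets the rules side by side and then counts the grade patterns that they treat differently.

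**Day 1.** Take an event on the dosing date whose recorded onset time is before the dose.

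- Protocol 11.1: pre-treatment, so not a TEAE.
- SAP 7.1: the worsening route covers only starts before the *date* of the first dose, so this event falls under the onset route. With no time rule it is a TEAE.
- SAP 13.5.4 does not resolve this. Its default to treatment-emergent applies where timing relative to drug cannot be determined, and here it can.
- SAP 13.2 allows date/times for baseline, so the SAP uses times elsewhere.

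**Benchmark.** Let *b* be the grade of an event ongoing at first dose, *c* its later grade on drug (with *c* > *b*), and *a* the grade of another pre-dose event of the same preferred term. Suppose the worsened event keeps its pre-dose start date.

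- Protocol 12.2.3.1: every such case has worsened, so it is a TEAE.
- SAP worsening route with the benchmark: a TEAE only if *c* > max(*a*, *b*).
- The two disagree when *b* < *c* ≤ *a*.

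CTCAE grades (Protocol 11.3.1), with pre-dose grades 1 to 4 and on-drug grades up to 5:

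- Worsening patterns: 4 values of *a* × (4 + 3 + 2 + 1) pairs (*b*, *c*) = 40.
- Denied patterns: for each *a* there are *a*(*a* − 1)/2 pairs with *b* < *c* ≤ *a*. For *a* = 1, 2, 3, 4 this gives 0 + 1 + 3 + 6 = 10.
- Share: 10/40 = 25% of patterns.

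Three-grade scale (mild, moderate, severe):

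- Worsening patterns: 3 × (2 + 1) = 9.
- Denied patterns: 0 + 1 + 3 = 4, or 4/9 = 44% of patterns.

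Example: a resolved grade 3 episode and an ongoing grade 1 event that rises to grade 2 on drug. The event has worsened (2 > 1) but does not exceed the benchmark (2 < 3).

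The count drops to zero in three situations:

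- Only one pre-dose event of the term was reported, so the benchmark is not triggered: 0 denied.
- The worsening is entered as a new event under Protocol 11.3.1 and the onset route prevails: 0 denied.
- Each event is compared with its own pre-dose severity: 0 of 40 and 0 of 9 denied.

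**Effect on a table.** One subject is 100/4 = 25 percentage points with the 4 enrolled, against 100/20 = 5 points at the planned 20.

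**The case against.** The best defence is that the SAP's onset route, together with the protocol's recording rules, already catches most worsening. Under Protocol 11.3.1 a grade change over several days is a new record dated at the change, so a rise on drug starts after the first dose and qualifies with no severity comparison. Under Protocol 11.1 a condition present at screening goes to medical history and becomes an adverse event only if it deteriorates, so deterioration on drug also has a post-dose start. The benchmark therefore reaches only events that arise between screening and first dose, at most 30 days, and that repeat under one term. On this view the benchmark sentence simply supplies the reference for the worsening route.

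Most of that stands, and it rules out some stronger conclusions that a reader might draw. The documents do not support saying that the benchmark generally hides worsening in subjects who had the symptom before dosing. Nor do they support reading 25% or 44% as the share of worsenings missed: the patterns are equally weighted cells, conditional on two pre-dose events of one term. Nor does the Day 1 rule attribute procedural events to the drug. TEAE status is about timing, relatedness is judged and tabulated separately, and the causality scale in Protocol 11.3.2 places events explained by study procedures under not related.

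Two things survive the defence. The benchmark is to be compared with treatment-phase events under the term, which could include new records, and the SAP does not say that the onset route prevails. If the benchmark did override it, a new on-drug episode no more severe than the benchmark would also be lost. Protocol 11.3.1 would then make the trigger easier to meet: one pre-dose event that falls from grade 2 to grade 1 becomes two events of the same term, and a return to grade 2 on drug only equals the benchmark. In addition, SAP 7.1 itself envisages a single record that changes grade, since it counts an event in two study parts if severity increases. A worsened event can therefore keep a pre-dose start date.

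**Conclusion.** Both departures are real, narrow and undeclared.

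The Day 1 departure affects only events that start on the dosing date with a recorded time before the dose. It over-counts TEAEs, the conservative direction.

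The benchmark departure under-counts. It requires at least two pre-dose events of one preferred term, one of them at least as severe as the on-drug grade, and a worsened event that keeps its pre-dose start date. If the benchmark is instead read as overriding the onset route, which the SAP does not rule out, the last condition falls away. In the first case 10 of 40 CTCAE patterns are affected (4 of 9 on three grades). How often such patterns occur cannot be derived from the documents.

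The 25-point shift assumes that all 4 enrolled subjects were dosed and that the reclassified subject has no other TEAE of that term.

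Severity is low. Protocol 12.2 plans no formal inference, and SAP 13.1 lists all data, so a reader can trace each event. What is at risk is the TEAE tables and TEAE listings, not the record of the events. The change is still worth making, because it aligns the primary safety endpoint with the protocol at almost no cost.

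**What to change.** Amend SAP 7.1 as follows:

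- An adverse event with onset after the first dose, up to the 30-day cut-off, is always a TEAE and is never overridden by the benchmark.
- An adverse event ongoing at first dose is a TEAE if its later severity exceeds its own severity at first dose. This replaces the comparison with the worst pre-dose event of the same term.
- On Day 1, use the recorded onset time where it is known. Where it is not, class the event as treatment-emergent, in line with the default in SAP 13.5.4.
- List any remaining departure from the protocol's definition in SAP section 15.

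The cost is a few sentences, slight programming work and small changes in TEAE counts. The Day 1 change can remove an event from the tables, and the severity change can add one.
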